12. STATISTICAL METHODS AND SAMPLE SIZE DETERMINATION BY

12.1 Description of analysis sets

12.1.1 Safety analysis set

All subjects who received at least 1 dose of ticagrelor and for whom any post-dose data are available will be included in the safety analysis set.

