2.2 Secondary objective

- To assess the safety and tolerability of co-administration of ticagrelor and cyclosporine in healthy male subjects by assessment of AEs, safety laboratory variables, physical examination, electrocardiogram (ECG), and vital signs

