5.2.1 Procedures for randomization

The randomization scheme will be generated by using the AstraZeneca global randomization system. Subjects will be randomized to 1 of 6 sequences on Day 1 of Visit 2.

	Period 1	Period 2	Period 3
Sequence 1	A	B	C
Sequence 2	A	C	B
Sequence 3	B	A	C
Sequence 4	B	C	A
Sequence 5	C	A	B
Sequence 6	C	B	A

Treatment A: a single oral dose of 600 mg cyclosporine dose (Neoral[®]) + a single oral dose of 180 mg ticagrelor

Treatment B: a single oral dose of 600 mg cyclosporine dose (Neoral[®])

Treatment C: a single oral dose of 180 mg ticagrelor

Randomization codes will be assigned strictly sequentially as subjects become eligible for randomization.

5.3 Procedures for handling subjects incorrectly enrolled or randomized or initiated on investigational product

Subjects who fail to meet the inclusion/exclusion criteria should not, under any circumstances, be enrolled or randomized. There can be no exceptions to this rule.

Where subjects who do not meet the selection criteria are randomized in error or incorrectly started on treatment, or where subjects subsequently fail to meet the study criteria post-initiation, a discussion should occur between the AstraZeneca Clinical Pharmacology Alliance (CPA) Physician and the Investigator regarding whether to continue or discontinue the subject from treatment.

The AstraZeneca CPA Physician is to ensure all such decisions are appropriately documented. In situations where an agreement cannot be reached, further administration of the investigational product should be stopped.

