5.5 Treatments

5.5.1 Identity of investigational product(s)

The investigational products used in this study are presented in Table 2.

Table 2 Identity of investigational products

Investigational product	Dosage form and strength	Manufacturer
Ticagrelor	90 mg tablets	AstraZeneca
Cyclosporine	100 mg capsules	

Ticagrelor 90 mg will be manufactured in accordance with Good Manufacturing Practice (GMP) and provided by AstraZeneca to the study center.

Details of the soft gelatine cyclosporine capsules can be found in the Neoral[®] package insert.

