12.1.2 PK analysis set

The PK analysis set will be a subset of the safety analysis set and will include only subjects who receive at least 1 administration of investigational product and have at least 1 post-dose plasma concentration measurement without important protocol deviations/violations or events thought to significantly affect the PK (eg, subject vomited at or before 2 times median t_{max} ; wrong dose administered; prohibited concomitant medication; etc).

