Appendix Date	

Appendix D
Optional Biomarker Research Samples

OPTIONAL BIOMARKER RESEARCH SYNOPSIS

A Single-Center, Open-Label, Randomized, 2-Treatment, 2-Period Cross-Over Study to Investigate the Effect of Cyclosporine on the Pharmacokinetics of Ticagrelor in Healthy Male Subjects

The research activities described in this appendix (including the collection and storage of body fluid samples), are optional for study centres as well as for individual healthy volunteers. These research activities will hereafter be referred to as “this research.” The clinical study protocol to which this document is appended will be referred to as “the main study.” The term “sample” means:

Plasma, Serum or Urine

This research will be performed only after the appropriate Ethics Committee/IRB has approved it. Informed consent for this research will be obtained using a separate Informed Consent Form from that used for the main study. All sections of the protocol for the main study also apply to this research.

Study center and number of patients who may be enrolled in this biomarker research

It is the intent of AstraZeneca to collect serum, plasma or urine samples from all Clinical Pharmacology studies conducted by the Clinical Pharmacology Alliance (CPA) to further the goal of improving biochemical markers that can be used to monitor or predict drug-induced organ damage. The goal will be to collect approximately 3000 such samples.

Objectives

Objective	Outcome variables
To analyze biological samples (eg, human plasma) for circulating biomarkers from consenting volunteers prior to drug treatment.	

Study design

It is proposed to collect a single serum, plasma or urine from each subject/healthy volunteer enrolled in the trial as optional samples for biomarker analysis. The type of sample to be collected will be determined at the outset of the trial. Provision of these samples for analysis will be optional for all healthy volunteers entering the study, and acceptance of this procedure will not be a requirement for participation in the main study.

The samples and data for optional biomarker analysis in this research will be coded. Each sample will be labelled with the study number and patient enrolment number (E-code). Only the investigator will be able to link the sample to the individual healthy volunteer. The samples and data will not be labelled with personal details.

Target population

All consenting volunteers in all centres participating in the main study.

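### The safety analysis set requires a ticagrelor dose, so a subject who stops after cyclosporine alone in Period 1 leaves the safety and PK sets, contrary to Sections 11.2 and 12.2.1

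*Protocol*

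**What the plan says.** Protocol Section 12.1.1 admits to the safety set "All subjects who received at least 1 dose of ticagrelor and for whom any post-dose data are available". Section 12.1.2 adds that "The PK analysis set will be a subset of the safety analysis set". Within that limit it asks for "subjects who receive at least 1 administration of investigational product and have at least 1 post-dose plasma concentration measurement", free of important deviations or events affecting the PK.

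On exposure, Section 5.5.1 states that "The investigational products used in this study are presented in Table 2", and that table lists both ticagrelor and cyclosporine. In Section 5.2.1, "Subjects will be randomized to 1 of 6 sequences on Day 1 of Visit 2". One of the three treatments there contains no ticagrelor: "Treatment B: a single oral dose of 600 mg cyclosporine dose". Sequences 3 (B A C) and 4 (B C A) give it first.

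Two other sections deal with subjects who leave early. Section 11.2 takes those who withdraw after dosing into the PK analysis if their concentrations are evaluable, and decides partial profiles case by case. Section 12.2.1 keeps a subject who withdraws within a period in the analyses until he stops. Neither requires a ticagrelor dose.

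**The concern.** A safety population should contain everyone exposed to a study drug. Here membership depends on which drug came first. A subject who takes 600 mg cyclosporine in Period 1 and then leaves, possibly because of an adverse event, is not in the set. A subject who takes ticagrelor, alone or with cyclosporine, in Period 1 and then leaves is in it.

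The secondary objective is "To assess the safety and tolerability of co-administration of ticagrelor and cyclosporine in healthy male subjects", and cyclosporine alone is one of the two single-drug references for judging co-administration. An early withdrawal on that reference could be missing from the summary counts when the same event on the other two treatments would be counted. The nesting also removes the subject's cyclosporine profile, although Section 11.2 would keep it.

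**Working it through.** **The plan's own figure.** Section 12.3 states 18 subjects for 90% power, with an intra-subject CV of 19%, true ratio 1.0, range 0.80 to 1.25 and two one-sided tests at 0.05.

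- Log-scale SD: s = √ln(1 + 0.19²) = √ln(1.0361) = 0.188.
- SE of a within-subject log ratio: s × √(2/18) = 0.188/3 = 0.063.
- Power, normal approximation: 2Φ(ln 1.25/0.0628 − 1.645) − 1 = 2Φ(1.91) − 1 = 94.4%.
- Power with t quantiles, integrating over the SD estimate: 92.1% with n − 2 degrees of freedom, 93.3% with 2n − 4. The smallest n reaching 90% is 17 in both cases.

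The stated 18 is therefore adequate and slightly conservative. It counts completers, who all receive ticagrelor, so the set definition does not change it.

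**Who is excluded.** Status of a subject who stops after Period 1 and before the Period 2 dose, with post-dose data:

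| Sequences | Period 1 | Ticagrelor received? | Safety set (12.1.1) |
|---|---|---|---|
| 1, 2 | A | yes | in |
| 3, 4 | B | no | out |
| 5, 6 | C | yes | in |

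A B-first subject who goes on to A or C enters the set and keeps his Treatment B data. The exclusion therefore applies only to Sequences 3 and 4, and only before the second dose.

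**The sections side by side, for that B-only subject.**

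- Section 12.1.1: out.
- Section 12.1.2: out, by nesting. Its own condition of one administration of investigational product would have admitted him. Its demand for a plasma concentration is a second obstacle, because Sections 6.4.1 and 11.2 measure cyclosporine in whole blood. Table 4 budgets 13 × 2 samples per assay, that is, two of the three periods each, so it foresees no plasma assay under Treatment B.
- Section 11.2: in, if his concentrations are evaluable.
- Section 12.2.1: in until he stops, if he leaves within the period.

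These statements cannot all be followed.

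**How many.** Share starting with B: 2/6 = 33.3%. With balanced allocation (assumed) this is 18 × 2/6 = 6 subjects, or 26 × 2/6 = 8.7 (8 or 9) at the enrolment ceiling. The protocol gives no withdrawal rate, so w, the proportion stopping between the first dose and Period 2, is assumed. Expected loss = 8.67 × w; chance of at least one loss = 1 − (1 − w)^m, with m = 8 or 9.

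| w (assumed) | Expected lost | Chance of at least one |
|---|---|---|
| 2% | 0.17 | 15–17% |
| 5% | 0.43 | 34–37% |
| 10% | 0.87 | 57–61% |
| 15% | 1.30 | 73–77% |

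**The case against.** The strongest reply is that very little is lost, and most of it stands.

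- **Listings.** Section 12.2.1 puts all data in the listings and flags what is excluded. Section 12.2.3 lists SAEs and discontinuations due to AEs separately, and Section 6.3.4 requires every SAE to be reported. Only summary counts are at risk. Section 12.2.3 does not name the set it uses; that it is the safety set is a reasonable inference, since no other set is defined for that purpose.
- **Safety comparison.** A reader might infer that the Treatment B reference is materially biased. The protocol does not support that. Safety is secondary and descriptive, with no test or decision rule. The by-treatment wording in Section 12.2.3 belongs to continuous variables; the AE sentences do not specify tabulation by treatment.
- **Rates.** A reader might also picture one omitted withdrawal moving an AE rate on B from about 4% to zero. That needs about 25 exposures, no other such event on B, and a withdrawal caused by an AE. If all 8 possible withdrawals occurred, four after Period 1 and four after Period 2, exposures would average (26 + 22 + 18)/3 = 22 per treatment. The figure is a worst-case illustration.
- **Primary PK.** The ratios in Section 12.2.4 rest on intra-subject variability. A B-only subject offers no within-subject contrast, and withdrawals are replaced to reach 18 completers (Section 5.9). What goes is his part of the descriptive cyclosporine summaries and at most a little between-subject information in the mixed model.
- **Origin.** Appendix D still carries the title "2-Treatment, 2-Period Cross-Over Study to Investigate the Effect of Cyclosporine on the Pharmacokinetics of Ticagrelor in Healthy Male Subjects", and in such a design every first dose would contain ticagrelor. It is tempting to call Section 12.1.1 a leftover, but the documents do not say so and the point does not need it.

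None of this reconciles the sections. The rule is stated, not left open for a later analysis plan, and it omits dosed subjects according to the order of treatments.

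**Conclusion.** The point holds as an internal contradiction with a narrow effect. Section 12.1.1 excludes a dosed subject whose only treatment was cyclosporine, Section 12.1.2 carries the exclusion into the PK set, and Sections 11.2 and 12.2.1 say otherwise.

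The expected loss is about 0.2 to 1.3 subjects, assuming 26 enrolled, balanced allocation and 2% to 15% stopping before Period 2. Enrolment of 26 is a ceiling, so fewer may be exposed to the rule. Losing all 8 of the possible withdrawals this way would require nearly every B-first subject to leave early and no one else to do so; it is an outer bound, not an expectation.

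The consequence is possible undercounting in safety summaries and a thinner descriptive cyclosporine-alone profile. It does not hide data from listings, threaten a primary conclusion or change the sample size. It should be corrected but does not invalidate the plan.

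**What to change.** - **Section 12.1.1:** admit every subject who received one or more doses of investigational product, naming ticagrelor or cyclosporine, and who has any post-dose data. Summarise by treatment received.
- **Section 12.1.2:** keep the nesting, which then does no harm, and replace the plasma requirement with a post-dose concentration of the relevant analyte: plasma for ticagrelor and AR-C124910XX, whole blood for cyclosporine.
- **Sections 11.2 and 12.2.1:** confirm that both agree with the revised sets. With the two changes above they need no new rule.

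The cost is one sentence in each of two sections, with no extra subjects, visits or samples and no change to the power calculation. The change is best made before data are seen, so that it cannot appear to depend on who withdrew.

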12.1.2 PK analysis set

The PK analysis set will be a subset of the safety analysis set and will include only subjects who receive at least 1 administration of investigational product and have at least 1 post-dose plasma concentration measurement without important protocol deviations/violations or events thought to significantly affect the PK (eg, subject vomited at or before 2 times median t_{max} ; wrong dose administered; prohibited concomitant medication; etc).

12.2 Methods of statistical analyses

12.2.1 General principles

The statistical analyses will be performed using SAS[®], Version 9.2 or higher. Standard Operating Procedures and Work Instructions will be used as the default methodology if not otherwise specified.

Missing data will result in a reduced sample size for that parameter. No action will be taken to handle missing data.

No adjustment for multiplicity will be made.

A subject who withdraws prior to the last planned observation in a study period will be included in the analyses up to the time of discontinuation.

All data will be included in the data listings. Any data excluded from the summaries and statistical analyses will be flagged accordingly.

12.2.2 Subject characteristics

Continuous variables will be summarized using descriptive statistics (n, mean, standard deviation [SD], minimum, median, and maximum) in total. Categorical variables will be summarized in frequency tables (frequency and proportion) in total.

12.2.3 Safety and tolerability

All safety data will be listed in subject listings. Continuous variables (hematology, clinical chemistry, and vital signs) will be summarized using descriptive statistics (n, mean, SD, minimum, median, and maximum) by treatment and/or each scheduled assessment point, both as absolute values and as change from baseline. Categorical variables (urinalysis, ECG interpretation) will be summarized in frequency tables (frequency and proportion) by scheduled assessment point. Laboratory values and vital signs outside reference limits will be marked high (H) and low (L) where appropriate.

For laboratory data and vital signs assessments all repeat values will be included in the data listings. For calculation of descriptive statistics the following rules will be applied: for measurement time points before the first dose the last valid repeat value will be used; for measurement time points after the first dose the first valid value will be used; retake of a pre-dose value will not be used if taken after dose. Laboratory values below the detectable limit ($< X$) will be replaced by X when summarizing mean, SD etc.

Abnormalities found in physical examinations will be listed.

Adverse events will be summarized by Preferred Term and System Organ Class using the MedDRA.

The number of subjects who had any AEs, SAEs, discontinuation due to AEs (DAEs), OAEs, AEs with severe intensity, and AEs judged causally related to the investigational product by the Investigator will be summarized. Any SAEs and DAEs will be listed separately.

12.2.4 Pharmacokinetics

A listing of PK blood sample collection times as well as derived sampling time deviations will be provided. Plasma concentrations and PK parameters for ticagrelor and its metabolite will be summarized using appropriate descriptive statistics (ie, n, mean, SD, geometric mean, geometric coefficient of variation [CV], minimum, median, maximum) by analyte and treatment. The geometric mean is calculated as the exponential of the mean calculated from

data on a log scale. The CV% is calculated as $100 \cdot \sqrt{(\exp(s^2) - 1)}$ where s is the SD of the data on a log scale.

For descriptive statistics, plasma concentrations that are below LLOQ will be handled as follows:

- At a time point where less than or equal to 50% of the values are below the LLOQ (BLQ), all BLQ values will be set to LLOQ, and all descriptive statistics will be calculated
- At a time point where more than half of the values are BLQ, the mean, SD, geometric mean and CV% will be set to Not Determined (ND). The maximum value will be reported from the individual data, and the minimum and median will be set to BLQ
- If all values are BLQ at a time point, no descriptive statistics will be calculated for that time point. Not Applicable (NA) will be written in the field for SD and CV% and BLQ will be written in fields for mean, geometric mean, minimum, median, and maximum
- The number of BLQ values (n below LLOQ) will be reported for each time point

Graphical presentations will include mean (\pm SD) plasma concentration-time curves by treatment and individual subject plasma concentration-time curves over the PK sampling times. The PK parameters will be presented graphically by scatter plots comparing individual and mean PK parameters between treatments.

The PK parameters for ticagrelor, AR-C124910XX, and cyclosporine will be natural log-transformed prior to analysis. The natural log-transformed AUC and C_{\max} data will be separately analyzed using a mixed effects model with terms for treatment, period, and sequence as fixed effects and subject nested within sequence as a random effect. The estimated least squares means and intra-subject variability from the mixed effects model will be used to construct 90% confidence intervals (CIs) for the difference in means on the log scale between the 2 treatments. The treatment effect and its corresponding 90% CIs will be back-transformed using anti-logarithms to its original scale and reported as ratio of treatments (ticagrelor + cyclosporine / ticagrelor alone or ticagrelor + cyclosporine / cyclosporine alone).

- If the 90% CIs for both AUC and C_{\max} for the effect of cyclosporine on ticagrelor are entirely contained within the pre-specified range of 0.80 to 1.25 then it will be conclude that a single 600 mg dose of cyclosporine has no effect on the PK of ticagrelor
- Also, if the 90% CIs for both AUC and C_{\max} for the effect of ticagrelor on cyclosporine are entirely contained within the pre-specified range of 0.80 to 1.25, then it will be conclude that a single 180 mg dose of ticagrelor has no effect on the PK of cyclosporine

12.3 Determination of sample size

Based on a previous study (D5130C00047), the intra-subject CV for AUC and C_{\max} of ticagrelor and AR-C124910XX are estimated to be less than or equal to 19%. Using an intra-subject variability of 19%, a sample size of 18 subjects would provide 90% power that the 2-sided 90% CI for the ratios of interest (AUC and C_{\max}) of ticagrelor to that of ticagrelor administered with cyclosporine would be completely contained within the pre-specified equivalence range of 0.80 to 1.25. Twenty-six subjects would be enrolled to allow for drop-outs. These calculations were based on two 1-sided tests at an alpha level of 0.05, assuming a true ratio of 1.0.

13.2 Overdose

There is currently no known antidote to reverse the effects of ticagrelor, and ticagrelor is not expected to be dialyzable. Treatment of an overdose should follow local standard medical

practice. Bleeding is the expected pharmacologic effect of excessive ticagrelor dosing, if bleeding occurs, appropriate supportive measures should be taken.

Ticagrelor is well tolerated in single doses up to 900 mg. Gastrointestinal toxicity was dose-limiting in a single ascending dose study. Other clinically meaningful adverse effects which may occur with overdose include dyspnea and ventricular pauses.

In the event of overdose, observe for these potential adverse effects and consider ECG monitoring.

- An overdose with associated AEs is recorded as the AE diagnosis/symptoms on the relevant AE modules in the eCRF and on the Overdose eCRF module
- An overdose without associated symptoms is only reported on the Overdose eCRF module

If an overdose on an AstraZeneca investigational product occurs during the course of the study, then the Investigator or other study center personnel will inform appropriate AstraZeneca representatives **within 1 day**, ie, immediately but no later than **the end of the next business day** of when he/she becomes aware of it.

The designated AstraZeneca representative works with the Investigator to ensure that all relevant information is provided to the AstraZeneca Patient Safety data entry site.

For overdoses associated with SAEs, standard reporting timelines apply, see Section 6.3.4. For other overdoses, reporting should be done within 30 days.

13.3 Pregnancy

All outcomes of pregnancy should be reported to AstraZeneca.

13.3.1 Maternal exposure

Women will not be included in this study.

13.3.2 Paternal exposure

Subjects should refrain from fathering a child or donating sperm during the study and 4 weeks following the last dose.

Pregnancy of a subject's partner will not be considered to be an AE. However, the outcome of all pregnancies (spontaneous miscarriage, elective termination, ectopic pregnancy, normal birth, or congenital abnormality) should be monitored and documented, if possible.

The outcome of any conception occurring from the date of the first dose until 4 weeks after the last dose should be followed up and documented.

Appendix B
Additional Safety Information

FURTHER GUIDANCE ON THE DEFINITION OF A SERIOUS ADVERSE EVENT (SAE)

Life threatening

‘Life-threatening’ means that the subject was at immediate risk of death from the AE as it occurred or it is suspected that use or continued use of the product would result in the subject’s death. ‘Life-threatening’ does not mean that had an AE occurred in a more severe form it might have caused death (eg, hepatitis that resolved without hepatic failure).

Hospitalization

Outpatient treatment in an emergency room is not in itself a serious AE, although the reasons for it may be (eg, bronchospasm, laryngeal edema). Hospital admissions and/or surgical operations planned before or during a study are not considered AEs if the illness or disease existed before the subject was enrolled in the study, provided that it did not deteriorate in an unexpected way during the study.

Important medical event or medical intervention

Medical and scientific judgement should be exercised in deciding whether a case is serious in situations where important medical events may not be immediately life threatening or result in death, hospitalisation, disability or incapacity but may jeopardize the subject or may require medical intervention to prevent one or more outcomes listed in the definition of serious. These should usually be considered as serious.

Simply stopping the suspect drug does not mean that it is an important medical event; medical judgement must be used.

Examples of such events are:

- Angioedema not severe enough to require intubation but requiring iv hydrocortisone treatment
- Hepatotoxicity caused by paracetamol (acetaminophen) overdose requiring treatment with N-acetylcysteine
- Intensive treatment in an emergency room or at home for allergic bronchospasm
- Blood dyscrasias (eg, neutropenia or anaemia requiring blood transfusion, etc) or convulsions that do not result in hospitalisation
- Development of drug dependency or drug abuse.

A GUIDE TO INTERPRETING THE CAUSALITY QUESTION

The following factors should be considered when deciding if there is a “reasonable possibility” that an AE may have been caused by the drug.

- Time Course. Exposure to suspect drug. Has the subject actually received the suspect drug? Did the AE occur in a reasonable temporal relationship to the administration of the suspect drug?
- Consistency with known drug profile. Was the AE consistent with the previous knowledge of the suspect drug (pharmacology and toxicology) or drugs of the same pharmacological class? OR could the AE be anticipated from its pharmacological properties?
- Dechallenge experience. Did the AE resolve or improve on stopping or reducing the dose of the suspect drug?
- No alternative cause. The AE cannot be reasonably explained by another aetiology such as the underlying disease, other drugs, other host or environmental factors.
- Rechallenge experience. Did the AE reoccur if the suspected drug was reintroduced after having been stopped? AstraZeneca would not normally recommend or support a rechallenge.
- Laboratory tests. A specific laboratory investigation (if performed) has confirmed the relationship?

A “reasonable possibility” could be considered to exist for an AE where one or more of these factors exist.

In contrast, there would not be a “reasonable possibility” of causality if none of the above criteria apply or where there is evidence of exposure and a reasonable time course but any dechallenge (if performed) is negative or ambiguous or there is another more likely cause of the AE.

In difficult cases, other factors could be considered such as:

- Is this a recognised feature of overdose of the drug?
- Is there a known mechanism?

Ambiguous cases should be considered as being a “reasonable possibility” of a causal relationship unless further evidence becomes available to refute this. Causal relationship in cases where the disease under study has deteriorated due to lack of effect should be classified as no reasonable possibility.

Clinical Study Protocol Appendix C

Drug Substance	Ticagrelor
Study Code	D5130C00074
Edition Number	1
Date	

**Appendix C
International Airline Transportation Association (IATA) 6.2
Guidance Document**

LABELING AND SHIPMENT OF BIOHAZARD SAMPLES

International Airline Transportation Association (IATA) classifies biohazardous agents into 3 categories (http://www.iata.org/whatwedo/cargo/dangerous_goods/infectious_substances.htm). For transport purposes the classification of infectious substances according to risk groups was removed from the Dangerous Goods Regulations (DGR) in the 46th edition (2005). Infectious substances are now classified either as Category A, Category B or Exempt. There is no direct relationship between Risk Groups and categories A and B.

Category A Infectious Substances are infectious substances in a form that, when exposure to it occurs, is capable of causing permanent disability, life-threatening or fatal disease in otherwise healthy humans or animals. Category A pathogens are eg, Ebola, Lassa fever virus:

- are to be packed and shipped in accordance with IATA Instruction 602.

Category B Infectious Substances are infectious Substances that do not meet the criteria for inclusion in Category A. Category B pathogens are eg, Hepatitis A, B, C, D, and E viruses, Human immunodeficiency virus (HIV) types 1 and 2. They are assigned the following UN number and proper shipping name:

- UN 3373 – Biological Substance, Category B
- are to be packed in accordance with UN3373 and IATA 650

Exempt - all other materials with minimal risk of containing pathogens

- Clinical trial samples will fall into Category B or exempt under IATA regulations
- Clinical trial samples will routinely be packed and transported at ambient temperature in IATA 650 compliant packaging (http://www.iata.org/whatwedo/cargo/dangerous_goods/infectious_substances.htm)
- **Biological samples transported in dry ice require additional dangerous goods specification for the dry-ice content**
- IATA compliant courier and packaging materials should be used for packing and transportation and packing should be done by an IATA certified person, as applicable

- Samples routinely transported by road or rail are subject to local regulations which require that they are also packed and transported in a safe and appropriate way to contain any risk of infection or contamination by using approved couriers and packaging / containment materials at all times. The IATA 650 biological sample containment standards are encouraged wherever possible when road or rail transport is used.

Clinical Study Protocol Appendix D

Drug Substance	Ticagrelor
Study Code	D5130C00074
Appendix Edition Number	1
